People exposed to chronic trauma face devastating effects to the brain and body. Chronically traumatized people become highly distressed when attending to emotional stimuli (Lanius et al. 2010), which can lead to feelings of detachment from their bodies, a phenomenon termed depersonalized dissociation. It is difficult to engage highly dissociative traumatized patients in trauma-focused treatment; however, these patients benefit from acquiring basic emotion regulation skills, including present-centeredness, which is a core feature of mindfulness meditation (Cloitre et al. 2012). Recently, mindfulness meditation practices which include body- and breath-focus elements have been shown to demonstrate short-term and long-term improvement in emotion regulation and clinical symptoms in people with PTSD (Earley et al. 2014, Seppala et al. 2014). Dissociation is characterized by deficits in accessing interoceptive states (Lanius et al. 2010), and dissociative states are shown to be incompatible with attending to aspects of one's physiological state, including the breath, since people with dissociation symptoms tend to feel immobile, paralyzed, and detached from their bodies (Galliano et al. 1993).

In order to address this issue, we will evaluate the effectiveness of a breath-focused exercise augmented with physiological feedback consisting of a vibrating element on the participant's sternum that vibrates in proportion to their breathing. The physiological feedback will provide bottom-up influences to augment cortical top-down influences. This feedback will act to enhance ability to attend to breath in people who otherwise cannot do that. This type of intervention has been useful in treating depressed and anxious patients to train attention away from threat stimuli (Bar-Haim 2010) towards environmental stimuli and towards positive stimuli amidst threat (Waters et al. 2012). Assessments for this project will be done in the context of

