Once participants express interest in the study, a study coordinator will contact them to assess whether they are still interested and administer a brief phone screen to confirm eligibility. The phone screen will ask about general physical health, identify potential contraindications of having an MRI scan, and assess if the participant is experiencing any PTSD symptoms. The interviewer will assess potential PTSD symptoms using the Modified PTSD Symptom Scale (MPSS) and the Primary Care PTSD Screen (PC-PTSD) (described more in depth in the measures section). If the participant is deemed eligible after the phone screen, they will be scheduled for an initial interview. The interview will be conducted by trained research assistants and will ask more in depth questions regarding psychiatric symptoms and life experiences.

If participants agree to be in the study and are determined to be appropriate for inclusion, they will begin to meet with their study clinician twice a week for three weeks after an initial assessment. A follow-up assessment will be conducted one month after the participant's treatment to examine any gains in attention, mindful focus, and interoceptive ability. To further assess any residual effects of the study intervention, an additional follow-up MRI session will be conducted between 1 month to 5 years after the final intervention session; this session will include additional assessments related to attention, learning, and subjective feedback about the intervention. The participants will receive instructions on a computer screen on how to conduct breath-focused mindfulness. Additionally, they will complete functional magnetic resonance imaging (fMRI) scans during the first session and the second follow-up session. Continuous EEG and psychophysiology data will also be collected during sessions 1-7. If participants are dissatisfied, they may withdraw from the study at any time.

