During the pre-intervention assessment, participants will complete clinical, neuropsychological, and interoception measures as well as EEG, psychophysiology, and fMRI. This session will last approximately 60 minutes and the participant will be compensated \$50. Visits 2-5 will involve breath-focused meditation for both augmented and non-augmented groups and concurrent measurements of EEG and psychophysiology. During visits 6-7, the non-augmented group will continue breath-focused meditation, whereas the augmented group will receive tapering levels of feedback, such that no physiological feedback will be present by the end of each session. Visit 8 will require the participant to complete the same tasks and surveys

completed during the first visit, as well as the MRI scan. These intervention visits will last 50 minutes each and the participant will be compensated \$20 per session for up to 7 sessions. The one-month follow-up will include only relevant self-report measures. This session will last approximately 60 minutes and the participant will be reimbursed \$50. Finally, the second follow up visit will last approximately 2 hours; this session will include 2 computer tasks completed inside the MRI scanner and self-report questionnaires. Compensation in the amount of \$50 will be provided for this follow-up.

Google Voice texting, a free texting service will be used to assist in study retention. Participants can miss intervention sessions due to forgetting their appointment times and missing reminder calls. The use of this texting service will allow participants to receive text message reminders of their appointments in addition the reminder calls.

Reimbursement to participants will be given via e-gift card. Participants will be emailed the e-gift card following each visit. E-gift cards will be purchased through Emory Express.

Measures:

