Data from this study will be based on self-report measures and behavioral tasks to be completed by participants. The self-report measures include the *Multiscale Dissociation Inventory* (MDI; Briere et al. 2005), the *Clinician Administered PTSD Scale* (CAPS) and *PTSD symptom Scale* (PSS), the *Kentucky Mindfulness Scale* (KIMS), the *Multidimensional Assessment of Interoceptive Awareness* (MAIA), and the *Kreek-McHugh-Schluger-Kellogg scale* (KMSK). The behavioral tasks include the breath focus task, rumination task, Affective Number Stroop task, Penn Computerized Neuropsychological Battery (Penn CNP). All self-report measures as well as the behavioral tasks will be administered during the pre- and post-interventions and the one-month follow-up session. During the last follow-up session, we will administer Affective Number Stroop and Visual Statistical Learning behavioral tasks as well as *Barriers to Needs Questionnaire* (BTNQ) self-report measure.

MDI. The MDI is a 30-item self-report test of dissociative symptomology and it measures six different types of dissociative response. The scales of the MDI are disengagement, depersonalization, derealization, emotional constriction/numbing, memory disturbance, identity dissociation, and total dissociation.

CAPS. The CAPS is a 30-item structured interview that can be used to make current and lifetime diagnosis of PTSD as well as assess PTSD symptoms over the past week. Questions also examine the onset and duration of symptoms, subjective distress, impact of symptoms on social and occupational functioning, improvement in symptoms since a previous CAPS administration, overall response validity, overall PTSD severity, and specifications for the dissociative subtype (depersonalization and derealization). The identification of an index traumatic event to serves as the basis for symptom inquiry. The full interview takes approximately 45-60 minutes to administer.

MINI Neuropsychiatric Interview is a semi-structured interview that will be used to assess for concurrent mood, substance, and psychotic disorders ([Sheehan et al., 1998](#)). The interview takes 30 minutes - 1 hour to administer.

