We have designed this study to have a final sample of 80 participants. The sample size of 80 was determined using a power analysis. Power was calculated using theoretical maximum detectable effect sizes given our samples. The proposed design, involving 40 completers in the active intervention arm and 40 completers in the control arm will yield sufficient power to detect effects at $d > .5$ for Aim 1) effects of the intervention of $d > .6$ and Aims 2 and 3) change in mechanism within the active group ($d > .6$) and across groups ($d > .6$). Although 80 is the minimum number needed to achieve statistically significant effects for our conditions of interest, we will enroll a higher number (110) with the expectation of attrition for some of these individuals.

All electronic data will be secured via an Emory secure network and password protection. Data will be managed electronically using REDcap. All participant data will be de-identified and all participants will be given a subject ID. Data gathered at each session will then be entered into REDcap with previous data and a hard copy of all data will be saved in a participant's folder. All hard copy data will be secured by storing it in a de-identified folder in a locked office in a locked

filing cabinet. Documentation regarding each session will also be kept as a hard copy in a participant's folder after being signed by both study researcher and licensed supervisor.

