Statistical analyses will not be conducted until the conclusion of the study when all measures and data have been collected. Analyses of behavioral data will be conducted using SPSS software. For analyses of fMRI activity, first-level, fixed-effect models will be created for each participant based on responses to each event of interest, which will be convolved with the hemodynamic response function. Events of interest include: breath-focus vs no breath focus; number congruent/number incongruent; error/missed responses. Motion regressors will be included in first-level models. Functional connectivity analyses will be conducted for affective challenge conditions including the incongruent trials from the Affective Number Stroop and rumination condition on the Rumination task. Within these conditions we will examine global connectivity indices (correlation of every voxel with every other voxel above and beyond physiological artifacts including respiration) within the proposed interoceptive network. These correlations will be transformed into standardized (z') indices for which the mean will be preserved per participant for group-level analyses.

Group (augmented vs non-augmented breath-focus mindfulness) by time (pre-post) mixed-effects analyses will be conducted on voxel-wise activity and mean global connectivity in the interoceptive network to examine intervention-related differences ($p < .05_{\text{corrected}}$). Functional relationships between different brain regions acquired over time, e.g., different brain regions, before and after intervention will be examined using Bayesian Belief networks (BNs). Mixed effects analysis [group x time (pre/post/follow-up)] will be used to examine clinical effects in 1) PTSD symptoms, measured by the CAPS (at 1 month) and PSS (immediately post-treatment); 2) Dissociative symptoms, measured by the MDI; 3) Mindfulness skills, measured by the Kentucky Mindfulness Scale.

Training:

All research assistants will be trained in all measures being used in the study and will fully understand the goals and purpose of the research proposed. These research personnel will be under the supervision of [name].

Data Management and Monitoring:

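### No symptom assessment is planned for participants who stop early, so loss that follows in-treatment worsening more in one arm could bias the group comparison in either direction

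*Combined protocol and SAP*

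**What the plan says.** **Schedule.** The Measures section fixes when the MDI, CAPS and PSS are given: "All self-report measures as well as the behavioral tasks will be administered during the pre- and post-interventions and the one-month follow-up session". The Procedure section matches this: "Visit 8 will require the participant to complete the same tasks and surveys" as at visit 1, and then "The one-month follow-up will include only relevant self-report measures". For visits 2–7 the documents list meditation, EEG and psychophysiology, the State Mindfulness Scale and one drug-use question. None of these is a PTSD or dissociation score.

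**Stopping.** The Procedure section states: "If participants are dissatisfied, they may withdraw from the study at any time". It does not separate stopping the sessions from leaving the study. It describes no exit assessment, and it neither invites early stoppers to visit 8 or the one-month session nor bars them.

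**Retention.** The same section plans reminder calls, text reminders and a payment for each visit.

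**Size and analysis.** The Data Analysis section sizes the trial on 40 completers per arm and adds: "we will enroll a higher number (110) with the expectation of attrition for some of these individuals". For the clinical outcomes it says: "Mixed effects analysis [group x time (pre/post/follow-up)] will be used to examine clinical effects". It ties the CAPS to one month and the PSS to the end of treatment.

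**The concern.** A mixed model uses whatever scores a participant has. If the only score is baseline, the model in effect predicts the later score from people in the same arm who began at the same level and stayed. That prediction is wrong if those who left had been doing worse than their baseline suggests.

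This is foreseeable here. Every session asks for attention to the breath, and the Supporting Research section says that "dissociative states are shown to be incompatible with attending to aspects of one's physiological state, including the breath". The arms may also differ in tolerance, because the same section predicts of the augmentation: "This feedback will act to enhance ability to attend to breath in people who otherwise cannot do that". That points to more intolerance without feedback, while dislike of the vibration would point to more with it.

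If worsening drives loss mainly in the augmented arm, the benefit is overstated. If it does so mainly in the control arm, the benefit is understated. Without later scores on leavers, the trial could not tell these cases apart on its own outcomes, and scores that were never collected cannot be recovered afterwards.

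**Working it through.** **Inputs from the documents.** 110 enrolled and 80 completers, 40 per arm (Data Analysis). The implied allowance is (110 − 80)/110 = 30/110 = 27.3%. No attrition rate is stated. Detectable effects are given as d above 0.5 and 0.6; I take 0.60 SD as the true effect.

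**What the model can and cannot correct.** I assume a likelihood fit that keeps everyone with a baseline score. Let π be the proportion of an arm that is lost, and Δ the amount by which leavers' true final symptoms exceed what baseline predicts from those who stayed. Then, with benefit counted as positive:

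estimated effect = true effect + π × Δ(augmented) − π × Δ(control)

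- Random loss: Δ = 0, so no bias.
- Loss driven by the baseline score in the model: Δ = 0, so no bias.
- Same mechanism and same loss in both arms: the two terms cancel.
- Loss following in-treatment worsening more in one arm: bias, with the sign set by the arm.

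**Assumed values for the size.** None of these comes from the documents. Simulation with 400,000 per arm; SD 1 at baseline, mid-treatment and post; baseline correlates r = 0.5 or 0.7 with later scores; mid–post correlation 0.8; true difference 0.30 SD at mid and 0.60 SD at post; equal loss in the two arms; loss logistic in standardized baseline-to-mid change, with slope 0.5, 1 or 2. Stopping itself does not alter the final score. Repeat runs agree to about 0.01 SD.

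| Loss pattern, 27.3% per arm | r = 0.5 (slopes 0.5, 1, 2) | r = 0.7 (slopes 0.5, 1, 2) |
|---|---|---|
| Worsening drives loss in augmented arm, random in control | 0.68, 0.73, 0.80 | 0.66, 0.70, 0.74 |
| Worsening drives loss in control arm, random in augmented | 0.53, 0.47, 0.40 | 0.55, 0.50, 0.46 |
| Same in both arms, or random | 0.60 | 0.60 |
| Loss driven by baseline, augmented arm only | 0.60 | 0.60 |

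In round terms the one-arm ranges are 0.65–0.80 and 0.40–0.55 SD, a bias of 0.05 to 0.20 SD. By the formula, Δ runs from 0.05/0.273 = 0.18 to 0.20/0.273 = 0.73 SD, which readers can judge for plausibility.

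**Partly shared loss.** With the control slope at half the augmented slope, the estimate is about 0.63–0.68 SD. With the roles reversed, symmetry gives about 1.20 − 0.68 = 0.52 to 1.20 − 0.63 = 0.57 SD.

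**Lower loss.** At 10% per arm, the one-arm ranges are 0.62–0.68 and 0.52–0.58 SD.

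**Effect of following up stoppers.** If a random half of leavers give the visit 8 score, the bias shrinks by a factor of about 0.5 × (1 − π)/(1 − π/2) = 0.5 × 0.727/0.864 = 0.42. So 0.05–0.20 becomes about 0.02–0.08 SD. The simulation agrees: 0.62–0.68 and 0.52–0.58 SD.

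**Effect of an in-treatment score.** A mid-treatment subscale (correlating 0.8 with the full score, missing for half of leavers) gives only 0.64–0.75 and 0.45–0.57 SD on its own. Added to follow-up of half of the leavers, it gives 0.62–0.66 and 0.55–0.59 SD.

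**The case against.** **The stated mechanism may act through baseline.** Dissociation is an entry criterion and is scored before treatment. If it is the more dissociative at entry who leave, the model for the MDI already allows for this, and the estimate stays at 0.60 SD. This stands. For the PSS and CAPS it holds as far as their own baseline carries the risk. The concern is confined to worsening after entry.

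**The one-arm case is extreme.** Both arms meditate on the same schedule, so some tolerance-related loss is likely in each. This stands too. In the partly shared case the bias is about 0.03–0.08 SD. The standard error with 40 per arm is √(2/40) = 0.22 SD unadjusted, or 0.22 × √(1 − 0.7²) = 0.16 SD if r = 0.7, so that bias is at most about half a standard error.

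**Retention is planned for.** Reminders and payments may keep loss low. They do not supply outcomes for people who stop anyway.

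**A mid-treatment scale is not needed in a three-week course.** Agreed: its absence is a defensible choice, and the figures show that adding one gains little.

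**Nothing bars stoppers from later visits.** True, but nothing invites them either, and the sample size is built around completers.

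**Conclusion.** The concern holds in a limited form. The documents plan for attrition and describe no symptom assessment for those who stop early. Whether bias follows depends on why people leave. There is none under random, baseline-driven or equal loss. Under the assumed values at 27% loss it is about 0.05–0.20 SD, in either direction, in the extreme one-arm case, and about 0.03–0.08 SD when partly shared. The correlations, slopes and loss mechanism are assumptions.

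A reader might infer more than the documents support:

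- *That the result will favour augmentation.* The documents give reasons for intolerance in either arm and no dropout reasons by arm.
- *That 27% is the expected or greatest loss.* It is a planning allowance. Actual loss may be higher or lower, and some may occur after visit 8.
- *That only completers are analysed.* The plan names a mixed-effects analysis and does not exclude anyone.
- *That nothing is known about leavers.* State mindfulness, EEG, psychophysiology and session records exist up to the point of leaving. They are not scores on the PTSD or dissociation outcomes.
- *That visit 8 is the critical point for every outcome.* For the CAPS it is the one-month visit.

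**What to change.** 1. Separate stopping the sessions from withdrawing from the study, in the protocol and in what participants are told.
2. Invite everyone who stops sessions to the visit 8 self-report scales (MDI and PSS) and to the one-month assessment, naming the CAPS there. Date both from the planned end of the three weeks, so that timing and the two-week PSS recall match those of completers.
3. Analyse these scores in the assigned arm, within the planned group-by-time model.
4. Report withdrawals with reasons, by arm.

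The cost is a few lines of text, a brief contact and the existing visit payments. If visit 8 is one of the seven sessions paid at $20, and the one-month session is paid at $50, that is $20 + $50 = $70 per person reached, the same as for a completer.

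The limits should be stated. Bias is reduced, not removed; some people will not be reached, those reached may differ from those not, and those who withdraw consent are not recovered. An MDI subscale at one early session is optional and adds little.

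### The power statement attaches both d > .5 and d > .6 to Aim 1 and gives no inputs that would support either value between arms

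*Combined protocol and SAP*

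**What the plan says.** All of the sample size reasoning is in the opening paragraph of Data Analysis. It fixes a final sample of 80, split 40 and 40, and says this "will yield sufficient power to detect effects at $d > .5$ for Aim 1) effects of the intervention of $d > .6". For Aims 2 and 3 it continues with "change in mechanism within the active group ($d > .6$) and across groups ($d > .6". The basis is described only as follows: "Power was calculated using theoretical maximum detectable effect sizes given our samples". The step from 80 completers to 110 enrolled is introduced by "Although 80 is the minimum number needed to achieve statistically significant effects for our conditions of interest".

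The planned models come later in the same section. For imaging: "Group (augmented vs non-augmented breath-focus mindfulness) by time (pre-post) mixed-effects analyses will be conducted on voxel-wise activity". For clinical outcomes: "Mixed effects analysis [group x time (pre/post/follow-up)] will be used to examine clinical effects in" PTSD symptoms, dissociation and mindfulness. The PTSD outcomes are each tied to one post-baseline time: "PTSD symptoms, measured by the CAPS (at 1 month) and PSS (immediately post-treatment". Specific Aims has no numbered aims and no effect sizes.

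**The concern.** A power statement should tell the reader which effect the trial can detect, for which contrast and under which model. Here Aim 1 has two candidate values and the supporting inputs are absent. This is the only justification for 80 completers and the only stated sensitivity. If Aim 1 is null, a reader cannot tell whether the result argues against effects of .5 or only against effects of .6 and above, or under which analysis.

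**Working it through.** **Inputs from the plan (Data Analysis).** 40 completers per arm; d > .5 and d > .6 for Aim 1; d > .6 for Aims 2 and 3, within the active arm and across arms; 110 enrolled.

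**Assumptions, because the plan states none of them.** Alpha .05, two-sided unless noted; 80% taken as sufficient power; Aim 1 taken as a between-arm contrast, since the plan says only that it concerns effects of the intervention.

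**1. Can 80 be reproduced?** For an unadjusted two-sample t-test, the noncentrality is d × sqrt(n/2) with 2n − 2 degrees of freedom. Completers needed in total:

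| | d = .5 | d = .6 |
|---|---|---|
| Two-sided, 80% power | 2 × 64 = 128 | 2 × 45 = 90 |
| One-sided, 80% | 2 × 51 = 102 | 2 × 36 = 72 |
| Two-sided, 90% | 2 × 86 = 172 | 2 × 60 = 120 |
| One-sided, 90% | 2 × 70 = 140 | 2 × 49 = 98 |

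None of these returns 80. The enrolment figure implies attrition of 30/110 = 27.3%, but the plan gives no attrition rate to check this against.

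**2. Power with 40 per arm, unadjusted (reference case).** The noncentrality is .5 × sqrt(20) = 2.236 or .6 × sqrt(20) = 2.683, with 78 degrees of freedom.
- Two-sided: power 0.598 at d = .5 and 0.755 at d = .6; minimum detectable d at 80% power 0.634.
- One-sided: 0.716 and 0.845; minimum detectable d 0.561.

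**3. Two occasions.** This covers the pre-post imaging analyses, or an outcome read at one post-baseline time. With pre-post correlation r, baseline adjustment multiplies the variance by 1 − r², and a change score multiplies it by 2(1 − r).
- Baseline-adjusted: 80% power at r = .615 for d = .5 (.5/sqrt(1 − .615²) = .634) and at r = .325 for d = .6 (.6/sqrt(1 − .325²) = .634).
- Change score: 80% at r = .689 for d = .5 and r = .553 for d = .6.

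**4. Three occasions.** Take a sustained d = .5, a baseline-adjusted mean of post and follow-up, baseline correlation r with each, and post/follow-up correlation q. The variance factor is (1 + q)/2 − r². At r = .5:
- q = .5: factor .75 − .25 = .50, power 0.878.
- q = .7: factor .85 − .25 = .60, power 0.813.
- q = .8: factor .90 − .25 = .65, power 0.782.

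Power falls to 80% at q of about .74. A two-degree-of-freedom group × time test under compound symmetry instead needs r = .661 for d = .5 or r = .511 for d = .6.

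**5. Within the active arm.** For a paired test with n = 40, the noncentrality is d × sqrt(40) with 39 degrees of freedom. If d is on the SD of change, power at d = .6 is 0.959 and the minimum detectable d is 0.454. If d is on the raw SD, 80% power needs .6/sqrt(2(1 − r)) ≥ .454, which gives r of about .13 or more. The plan does not say which scale it uses.

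**6. Meaning of 80.** In the reference case the smallest observed d reaching p < .05 is t(.975, 2n − 2) × sqrt(2/n): 0.445 with 40 per arm and 0.517 with 30 per arm. So 80 is neither necessary nor sufficient for significance.

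**The case against.** The best defence reads .5 as a general lead-in and the numbered items as the real targets. The list markers fit that reading, and both figures are lower bounds, so they are not logically exclusive. This stands as a possible reading. It does not settle the matter, because .5 then belongs to no listed contrast while still standing as a sensitivity claim for the design.

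A reader might infer from the 60% figure that the trial is underpowered, or that it needs 128 completers. The documents do not support that. The unadjusted t-test is not the planned analysis; the plan uses group × time mixed models, and steps 3 and 4 show that 40 per arm can support either value under plausible correlations. Measures also describes repeated administration: "All self-report measures as well as the behavioral tasks will be administered during the pre- and post-interventions and the one-month follow-up session".

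A reader might also infer that only .5 is in doubt. It is not: between arms, .6 also falls short of 80% in the two-sided reference case and needs its own model and correlation.

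The remarks on significance and on the maximum detectable effect can fairly be read as loose phrasing for the number of completers the power analysis calls for and for the smallest detectable effect. No design decision depends on either, so they are minor.

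**Conclusion.** The concern holds as a defect in the stated sensitivity, not as a demonstration of low power. Aim 1 carries two detectable effects, nothing else in the document resolves them, and neither is supported between arms as written. In the assumed reference case the choice separates 128 from 90 completers, a gap of 38, and 40 per arm detects d = 0.63 at 80% power. With baseline adjustment at two occasions, the stated values hold only from r of about .62 (d = .5) or .33 (d = .6). The three-occasion results need an effect present at both post-baseline times. Every figure rests on assumed alpha, sidedness, power, model and correlation. The ambiguity itself rests on the text alone. The within-arm d > .6 is comfortably powered if it is on the SD of change; on the raw SD that depends on the correlation.

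**What to change.** Replace the sentence with one minimum detectable effect for each contrast: Aim 1 (between arms, if that is what is meant), Aims 2 and 3 within the active arm, and Aims 2 and 3 between arms. For each, give the outcome and time point, model, alpha, sidedness, power and assumed correlation.

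- If no adjustment was assumed, with two-sided .05 and 80% power, state that 40 completers per arm give a minimum detectable effect of d = 0.63 between arms and d = 0.45, on the SD of change, within the active arm.
- Keep .5 or .6 between arms only with the model and correlations that support it. For d = .5, one such basis is a baseline-adjusted mean of post and follow-up with a sustained effect, r = .5 and a post/follow-up correlation up to about .74.
- These figures are for a single test at .05. The corrected voxel-wise tests need their own statement.
- Minor wording: change maximum to minimum detectable effect, and describe 80 as the number of completers the power analysis requires.

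The cost is protocol wording only. Enrolment and analyses do not change, though the stated between-arm sensitivity may become slightly less favourable.

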stressful tasks, emotional stimuli, and non-ideal conditions in order to resemble the patients' chaotic lives. Breath-awareness will be examined in isolation for the following reasons: 1) we are working to optimize an aspect of mind-body connection that could benefit from this specific technique, 2) we are examining whether targeting a specific mechanism with a specific theory-driven intervention is possible, and 3) breath focus appears to have specific health-positive effects that extend beyond philosophical tenets which we would like to test.

Research suggests that there exists an “interoceptive network” of brain structures that are involved with the perception of phenomena internal to the body (Craig 2002, Craig 2009). The central node of this network is the insula and it includes motor and somatosensory cortices (SMA), as well as regions associated with attention and representation of the self (Frontal pole; Anterior cingulate cortex, ACC). Connectivity between ACC and insular regions is also proposed to play a role in the proper detection of physiological and corresponding emotional states (Taylor et al. 2009). We will examine connectivity between additional nodes of the interoceptive network, the orbitofrontal cortex (OFC) and somatosensory cortex (SSC), as participants engage in a heartbeat counting task and an attention to emotion task (the Affective Number Stroop) as they attend to their breath. We anticipate that the physiologically-augmented meditation intervention will produce greater connectivity between nodes of the interoceptive network during exposure to emotional distractors in this task.

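### The hypothesis concerns connectivity between nodes of the interoceptive network, but the index given a group-by-time test also averages voxel pairs inside the same node, so its result cannot be read as a between-node effect

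*Combined protocol and SAP*

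**What the plan says.** The protocol's Supporting Research section lists the nodes of the network: the insula as the central node, motor and somatosensory cortices, frontal pole and anterior cingulate, with orbitofrontal and somatosensory cortex as additional nodes. It then predicts that the augmented intervention "will produce greater connectivity between nodes of the interoceptive network during exposure to emotional distractors in this task".

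The Data Analysis section defines the connectivity index as the "correlation of every voxel with every other voxel above and beyond physiological artifacts including respiration", computed "within the proposed interoceptive network". The correlations are "transformed into standardized (z') indices for which the mean will be preserved per participant for group-level analyses". At group level, augmented versus non-augmented by pre-post "mixed-effects analyses will be conducted on voxel-wise activity and mean global connectivity in the interoceptive network", at a corrected .05 level.

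The same section adds that functional relationships between brain regions before and after the intervention will be examined with Bayesian Belief networks. It names no comparison of the two arms, no edge or summary measure, and no threshold for that analysis.

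**The concern.** The quantity predicted and the quantity tested differ. The prediction is about links between distinct regions. The index is an average over every voxel pair in the network, and some of those pairs lie inside one region. Same-node pairs carry no information on the prediction, yet they enter the mean with a weight set by node size.

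Two errors of interpretation follow. A rise in coherence within, say, the insula could give a significant group-by-time result that is then reported as support for the between-node hypothesis. Conversely, a genuine between-node rise could be weakened in the average if same-node pairs stay put. The matter is confined to a mechanism outcome. The clinical outcomes (CAPS, PSS, MDI, Kentucky Mindfulness Scale) are not affected.

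**Working it through.** **Inputs from the documents (Data Analysis).** 40 completers per arm; detectable mechanism effect across groups d > .6. Power is called sufficient, with no percentage or sidedness. The correction method for the imaging tests is not named. **Not in the documents:** node masks, volumes and laterality; the SD of the index; how within-node and between-node means vary together. All values used for these below are assumptions.

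**Step 1: the plan's own figure.** For a two-sample t test with d = .6, 40 per arm and two-sided .05 (no multiplicity correction), the noncentrality is .6 × √(40/2) = 2.68 on 78 df. Power is 75.5% (76.5% by the normal approximation). One-sided it is 84.5%. By the normal approximation, the d detectable with 80% power is .63 two-sided and .56 one-sided. So .6 is roughly consistent with 40 per arm, but without a stated target it cannot be strictly reproduced.

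**Step 2: what the index measures.** Let H be the share of voxel pairs in the same node, B the mean z' over different-node pairs and W the mean z' over same-node pairs. Then

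index = (1 − H) × B + H × W,

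and the group-by-time contrast splits the same way: Δindex = (1 − H) × ΔB + H × ΔW. If ΔB = 0 and ΔW is not, the contrast equals H × ΔW, which is not zero. This needs no assumption about SDs or node sizes beyond H > 0.

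**Step 3: size of H.** With many voxels, H is about the sum of squared node-size fractions.

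**Step 4: simplest dilution case.** Assume ΔW = 0 and the SD of the index equal to that of B. Then d = .6 × (1 − H). Power is two-sided at 40 per arm.

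| Assumed node sizes | H | d | Power |
|---|---|---|---|
| 6 equal | 6 × (1/6)² = .167 | .50 | 59.8% |
| 5 equal | 5 × .2² = .20 | .48 | 56.4% |
| One at 40%, four at 15% | .16 + 4 × .0225 = .25 | .45 | 51.1% |
| One at 50%, four at 12.5% | .25 + 4 × .0156 = .31 | .41 | 44.5% |

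**Step 5: relax those assumptions.** Let g = ΔW/ΔB, k = SD of W divided by SD of B, and r = the correlation of W and B. Then

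d = .6 × (1 − H + H × g) / √[(1 − H)² + H²k² + 2H(1 − H) × r × k].

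| H | k | r | g | d | Power |
|---|---|---|---|---|---|
| .20 | 1 | 0 | 0 | .58 | 72.9% |
| .20 | 1 | .5 | 0 | .52 | 63.8% |
| .20 | 1 | .5 | .5 | .59 | 74.0% |
| .20 | 1 | .5 | 1 | .65 | 82.4% |
| .31 | 1.5 | .9 | 0 | .37 | 36.5% |

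For H = .20, k = 1 and r = .5, the divisor is √(.64 + .04 + .16) = .917, so g = 0 gives .48/.917 = .52. Power therefore runs from about 37% to above the 75.5% starting point, depending on quantities the documents do not give.

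**The case against.** The strongest objection is that a reader might infer that pooling will dilute the effect and leave the imaging test underpowered. The documents do not support that. Dilution of the raw effect requires same-node pairs to change less than different-node pairs. The Supporting Research section also expects explicit somatic cuing to restore the function of the insula, so some within-insula change is plausible. The unchanged-SD assumption in Step 4 amounts, when k = 1, to a correlation of 1 between the two means, which is the least favourable value for k = 1. This objection stands: the power figures are illustrations, not findings.

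The node count is also unsettled. If left and right regions count separately, giving 10 to 12 equal nodes, H is 8% to 10%. Even on Step 4's assumptions, d is then .54 to .55 and power about 66% to 68%. On every layout in Step 4 most pairs (69% to 83%) are between nodes. In addition, d = .6 is stated for change in mechanism generally and is not tied to this index.

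A reader might also infer that between-region relationships are never examined. That is not so, because the Bayesian Belief networks address them. With no arm comparison, summary measure or threshold, however, they narrow the gap without supplying a test of the hypothesis.

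Two supporting arguments do not add to the case. High baseline correlation among neighbouring voxels does not by itself bias a comparison of change between arms. That larger nodes count for more is a matter of weighting, and equal weights would give small, noisy nodes more influence.

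None of this touches Step 2: the tested mean mixes two quantities, and only one of them is hypothesised.

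**Conclusion.** The point holds as a mismatch between hypothesis and test. The only connectivity outcome with a stated group-by-time test pools same-node and different-node pairs, so a positive result would not by itself show a between-node effect and a null result would not exclude one. This follows from the definition of the index.

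Loss of power is possible but neither certain nor measurable from the documents. The fall to about 60% to 45% applies only with 17% to 31% same-node pairs, no same-node change and an unchanged SD, and is computed without multiplicity correction. The importance is minor: it concerns how one mechanism result is interpreted, and it is cheap to resolve.

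**What to change.** Define the node masks before analysis, including whether left and right regions are separate nodes and how somatosensory cortex, listed both in the core network and as an additional node, is counted. Name as the test of the between-node hypothesis the mean z' over voxel pairs from different nodes, or over correlations of node-mean time series, in the same group-by-time mixed model. Report the within-node mean and the all-voxel global index as secondary, so that a reader can see where any change arises. Weighting node pairs equally is optional; whichever weighting is used should be stated in advance.

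The cost is fixing the masks beforehand, one extra averaging step, and moving the global index to secondary status. No further scans or participants are needed. Because the Data Analysis section defers all statistical analyses to the end of the study, the change can be written down before results are seen.
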